11.5 Prior and Concomitant Medications and Procedures

Baseline AED medications are defined as AED medications that started prior to and are ongoing at the time of the first dose.

Concomitant AED medications are defined as AEDs that started prior to and are ongoing at the time of the first dose of study medication or started after the first dose of study medication.

Prior medications are defined as non-AED medications with a start date and stop date prior to the first dose of study medication.

Concomitant medications are defined as non-AED medications with a start date on or after the first dose of study medication (Day 1) or started prior to and are ongoing at the time of the first dose of study medication.

Concomitant procedures are defined as procedures with a start date on or after the first dose of study medication (Day 1).

Prior and concomitant therapies will be coded to a World Health Organization Drug Dictionary (WHO DD) term including ATC classification (Version March 2016 or a later version available at the time of data cut-off). A by-subject listing of baseline AEDs, concomitant AEDs, prior and concomitant non-AEDs use, and concomitant procedures will be produced.

The use of baseline and concomitant AEDs, prior non-AEDs, and concomitant non-AEDs will be summarized by safety evaluable subgroup and overall for subjects in the safety population. The number and percentage of subjects taking each medication will be presented by ATC Classification.

In addition, a summary table for:

- Number of baseline AEDs (0, 1, 2,->2)
- Number of baseline AEDs per subject (mean, standard deviation, median, minimum, and maximum number of AEDs)

will be prepared for safety population (overall and by safety evaluable subgroups).

11.6 Medical and Seizure/Epilepsy History

Medical history will be summarized (number and percentage of subjects) by body system overall and by safety evaluable subgroups using safety population. The medical history data will also be presented in a by-subject listing. Female reproductive history will be presented in a by-subject listing.

Epilepsy classification and history of seizures by type, current and past seizures will be summarized overall and by safety evaluable subgroups for safety population and will be included in by-subject listings.

Duration of epilepsy diagnosis (years) will be estimated as the number of years between year of diagnosis and date (year) of the informed consent

11.7 EEG, MRI or CT Scan Results

All EEG, MRI or CT Scan results will be listed by-subject. These results will also be summarized at baseline overall and by safety evaluable subgroups for the safety population.

12 PHARMACOKINETIC AND PHARMACODYNAMIC ENDPOINTS AND ANALYSIS

Time and date of each blood draw and dosing records (time/date/dose) of YKP3089 and AEDs prior to each blood draw will be recorded on the eCRF and other appropriate forms.

Plasma samples will be assayed for YKP3089 and AEDs at a specified bioanalytical laboratories using previously validated methods. Assay methodologies will be detailed in separate bioanalytical reports.

Subjects receiving phenobarbital or phenytoin: Samples will be obtained from subjects taking phenobarbital or phenytoin at any global sites. At Visit 2, a single trough level of phenytoin or phenobarbital will be obtained. At Visits , 4, 5, 6, 7 and 8, two blood samples will be collected for the determination of phenobarbital or phenytoin plasma levels. At Visits 8 and 9, two blood samples will be collected for YKP3089 depending on stability of dosing (stable dose all AEDs including YKP3089 for prior 2 weeks).

Subjects taking other taking concomitant AEDs other than phenobarbital or phenytoin : Samples will be obtained from subjects taking concomitant AEDs other than phenobarbital or phenytoin at US sites. At Visit 2, a single blood sample will be drawn to determine trough level if the subject is taking one of the followings, oxcarbazepine, topiramate, lamotrigine, lacosamide, clobazam, perampanel and levetiracetam. At Visit 8 and/or 9, two blood samples will be drawn from the same subjects to determine plasma levels of YKP3089, oxcarbazepine, topiramate, lamotrigine, lacosamide, clobazam, perampanel and levetiracetam. Collect at visit 8 and/ or 9 depending on stability of dosing (stable dose all AEDs including YKP3089 for prior 2 weeks).

The collection schedule is included in the table below:

Cohort →	Subjects taking Phenytoin or Phenobarbital	Subjects taking AEDs other than Phenytoin or Phenobarbital
Blood collection for YKP3089 levels	Visits 8 and/or 9	Visits 8 and/or 9
Blood collection for phenytoin or phenobarbital levels	Visits 2*, 4, 5, 6, 7 and 8	Not Applicable
Blood collection for concomitant AEDs (other than phenytoin or phenobarbital) levels	None	Visits 2*, 8 and/or 9

* At Visit 2, one sample will be collected; at all other visits, two samples will be collected

Plasma concentrations of YKP3089 and of concomitant AEDs measured in samples collected in this study will be combined with clinical data from previous studies to generate and validate population pharmacokinetic model for YKP3089. Relevant concomitant AEDs will be tested as covariates to evaluate their possible effect on YKP3089 PK. In addition, the effect of YKP3089 on the PK of relevant AEDs (like lamotrigine or lacosamide for instance) will be assessed if deemed appropriate. These analyses will be included in the separate report.

For the CSR, summary tables including descriptive statistics (mean, SD, median, minimum, maximum) for plasma concentrations of the concomitant AEDs and for plasma concentrations of the YKP3089 as per Central Lab results will be prepared by the planned collection timepoints.

13 SAFETY ANALYSIS

Safety analyses will be performed using safety evaluable set. Separate by-subject AEs and SAEs listings will be prepared for screen failures.

Safety will be assessed by the frequency, severity of adverse events, as well as by clinical laboratory test values, 12-lead ECG recordings, vital sign measurements, physical and neurologic examinations, and the Columbia-Suicide Severity rating Scale (C-SSRS).

13.1 Analysis of Adverse Events (treatment -emergent, non-serious, serious, and deaths)

Adverse events will be coded to a Medical Dictionary for Regulatory Activities Terminology (MedDRA) version 20.0 or later version available at the time of data cut-off. Verbatim description and the MedDRA System Organ Class (SOC) and Preferred Term for all adverse events will be contained in the subject data listings of the clinical study report.

For adverse events with partial start date (i.e., with only month and year are recorded), the following imputation rule will be applied: 15th of the month or fist dose date which one comes later. The imputed date will be used to derive TEAE analysis flag. The actual collected date will be displayed in all AE data listings.

All reported adverse events (regardless of treatment-emergent or not) will be included in a by- subject adverse event listing, with separate by-subjects listings for adverse events and serious adverse events reported for screen failures.

Only treatment-emergent adverse events will be included in summary tables.

Treatment emergent adverse events (TEAE) are defined as AEs with onset after the start of study medication, up to last dose date of study medication + 14 days (or analysis cut-off date whichever comes first), or onset before study medication and worsened after starting study medication, up to last dose date of study medication + 14 days (or analysis cut-off date whichever comes first).

An adverse event is regarded as related to study medication if the relationship to study medication is definite, probable, or possible. Adverse events with missing

relationship will be assumed to be treatment related. Adverse events with missing severity will be assumed to be severe in order to perform the most conservative statistical analysis.

Severe adverse events and adverse events related to treatment will be summarized overall and by safety evaluable subgroups.

TEAE Incidence will be computed as number of subjects with AE/ number of subjects in each reporting group (%).

Incidence of TEAEs leading to study drug discontinuation will report only TEAEs with Action Taken = study drug discontinuation.

In TEAE summary tables, system organ classes (SOCs) will be presented in alphabetical order and preferred terms within each SOC will be presented in descending order of frequency in overall YKP3089 group within each SOC, unless specified otherwise.

The planned summary of adverse events tables are listed below:

- Incidence of treatment-emergent adverse events by MedDRA System Organ Class and Preferred Term
- Incidence of treatment-emergent adverse events (TEAEs) in descending order of frequency in all YKP3089 group.
- Incidence of severe treatment-emergent adverse events by MedDRA System Organ Class and Preferred Term
- Incidence of treatment-emergent adverse events related to study medication by MedDRA System Organ Class and Preferred Term
- Incidence of treatment-emergent adverse events by MedDRA System Organ Class, Preferred Term, and by maximum severity
- Incidence of treatment-emergent adverse events leading to study drug discontinuation by MedDRA System Organ Class and Preferred Term
- Incidence of treatment-emergent serious adverse events by MedDRA System Organ Class and Preferred Term

Deaths, other serious adverse events, and adverse events leading to study drug discontinuation, will be listed including the safety evaluable subgroup and YKP3089 dose (if applicable) at onset, start and stop dates of the adverse event, and days on study relative to the start of the study. Details of listings that will be provided for the safety evaluable analysis population are as follows:

- Listing of subjects who died;
- Listing of subjects with treatment-emergent serious adverse events;
- Listing of subjects with non treatment-emergent serious adverse events;
- Listing of subjects with treatment-emergent severe adverse events;
- Listing of subjects with treatment-emergent adverse events leading to study drug discontinuation.

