- The subject may take the first dose of the study medication the same day or the next morning. If the investigator wants to observe the subject after the first dose at the clinic, the first dose can be administered at the site after all other Visit 2 procedures have been completed
- Schedule a return to occur in 2 weeks for Visit 3
- Dispense laminated Hypersensitivity Information safety card
- Call subject in approximately one week to check for any adverse events

9.1.3 *Visit 3, Day 15*

As shown in [Table 1](#), the following will be performed at Visit 3:

- Record vital signs
- Perform limited physical exam for signs of hypersensitivity such as rash, swelling, lymphadenopathy and fever
- Conduct brief neurologic examination if required
- Draw blood for laboratory safety assessment
- Administer C-SSRS (Since Last Visit version)
- Record concomitant medications
- Perform drug accountability
- Record AEs
- Dispense study drug as instructed by IWRS
- Schedule a return to occur in 2 weeks for Visit 4
- Check and dispense laminated Hypersensitivity Information safety card
- Call subject in approximately one week to check for any adverse events

9.1.4 *Visit 4, Day 29*

As shown in [Table 1](#), the following will be performed at Visit 4:

- Record vital signs
- Measure weight
- Perform limited physical exam for signs of hypersensitivity such as rash, swelling, lymphadenopathy and fever

- Conduct brief neurologic examination if required
- Administer C-SSRS (Since Last Visit version)
- Draw blood for laboratory safety assessment
- Record concomitant medications
- Perform drug accountability
- Record AEs
- For subjects taking phenytoin or phenobarbital, draw blood for phenytoin or phenobarbital levels. Two blood samples will be collected: For subjects taking phenytoin or phenobarbital in the morning and coming into the visits in the morning, the first blood draw will be collected upon subjects' arrival to the study unit; the second blood draw should be collected within 30 minutes to 2 hours after the medication is taken.
- Dispense study drug as instructed by IWRS
- Schedule a return to occur in 2 weeks for Visit 5
- Check and dispense laminated Hypersensitivity Information safety card
- Call subject in approximately one week to check for any adverse events

9.1.5 *Visit 5, Day 43*

As shown in Table 1, the following will be performed at Visit 5:

- Record vital signs

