8.2 Safety and Tolerability Measures

8.2.1 Adverse Events

Adverse event (AE) assessments will be recorded on the Adverse Events eCRF. The term AE is used to include both serious and non-serious AEs.

Adverse events will be assumed to be treatment emergent unless (through comparison of full or partial dates) the onset date of the adverse event is specified as outside the treatment period or its exclusion from the treatment emergent period can be definitely ascertained from the end date or available month and year components of either of the start or end dates. An AE is also considered treatment emergent if the onset date is before the start of study treatment [Visit 2 /Day 1 + 1] but the severity worsened following that. If the AE onset date is missing or partial, the date will be compared as far as possible with the date of first dose of study treatment. Treatment emergent AEs (TEAEs) occurring during the study treatment period from the first dose of study drug medication up to and including 14 days after the end of treatment (i.e., not present at baseline or worsened in severity following start of treatment) will be reported as TEAEs.

For each AE, the following will be collected: the verbatim term for the AE, start date, end date or indication of ongoing, severity, indication of Serious AE, SAE criterion, relationship to study drug, action taken, and outcome. AEs will be coded using MedDRA version 20.0.

The onset day of the AE will be the difference between the date of onset of the AE and the date the study drug medication was first dispensed + 1. The duration of the AE will be the difference between the end date of the AE and its onset date + 1.

AE relationship to study drug can be classified by the investigator as definite, probable, possible, remote or unrelated. AEs severity can be rated as mild, moderate or severe.

AEs are classified as serious or non-serious. A serious adverse event (SAE) is any AE that is:

- Fatal
- Life-threatening
- Requires or prolongs hospital stay
- Results in persistent or significant disability or incapacity
- A congenital anomaly or birth defect
- An important medical event

Adverse events (including SAEs) are collected through the length of study for all enrolled subjects and for screen failures.

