10.3 Visit Windows for Safety Analyses

The table below presents the visits assigned for safety analyses corresponding to the range of treatment study days (window) during which an actual visit (scheduled or unscheduled) may occur. Note that the windows defined for statistical analysis are different from the ones defined in Protocol Section 9.

Visit windows for laboratory tests, vital signs, and for Columbia Suicide Symptoms and Signs Rating Scale (CSSRS):

Derived Visit	Target Study Day [1]	Window [2]
Baseline (for laboratory tests and vitals)	Day 1	Days <= 1
Baseline (for C-SSRS)	Screening (Visit 1)	NA
Visit 2 (for C-SSRS)	Day 1	Days = 1
Visit 3	Day 15	>= Day 2 to <= Day 22
Visit 4	Day 29	>= Day 23 to <= Day 36

Visit 5	Day 43	>= Day 37 to <= Day 50
Visit 6	Day 57	>= Day 51 to <= Day 64
Visit 7	Day 71	>= Day 65 to <= Day 78
Visit 8	Day 85	>= Day 79 to <= Day 92
Visit 9	Day 99	>= Day 93 to <= Day 106
Visit 10	Day 113	>= Day 107 to <= Day 128
Visit 11	Day 143	>= Day 129 to <= Day 173
Visit 12	Day 203	>= Day 174 to <= Day 233
Visit 13	Day 263	>= Day 234 to <= Day 314
Visit 14	Day 365	>= Day 315 to <= Day 410
3 Months after 1 Year Treatment	Day 456	>= Day 411 to <= Day 501
6 Months after 1 Year Treatment	Day 547	>= Day 502 to <= Day 592
9 Months after 1 Year Treatment	Day 638	>= Day 593 to <= Day 684
12 Months after 1 Year Treatment	Day 730	>= Day 685 to <= Day 775
15 Months after 1 Year Treatment	Day 821	>= Day 776 to <= Day 866
18 Months after 1 Year Treatment	Day 912	>= Day 867 to <= Day 957
21 Months after 1 Year Treatment	Day 1003	>= Day 958 to <= Day 1049
24 Months after 1 Year Treatment	Day 1095	>= Day 1050 to <= Day 1112
Visit 15 (14-day follow-up)	Day of the last dose of study	>= day of the last dose of study drug+14

	drug+14 days	
Termination Visit [3]	Termination Visit during treatment period	

[1] Relative to the date of the first dose of study drug. For example, Day 1 = the date of the first dose of study drug.

[2] The study days evaluated for windows of visits during treatment period are on or prior to the last dose day.

[3] For subjects who decide not to continue in the study at any time (i.e., eCRF check box for “Continuing” is answered ‘No’), the Termination Visit is performed (as per Protocol Section 9.1.14). This is available for entry at any time as a separate visit on eCRF. The study day for the termination visit will be assigned relative to the first dose of study drug.

Visit windows for ECG measurements:

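### For AEs with only month and year of onset, SAP 8.2.1 and 13.1 set the treatment-emergent flag by different rules without precedence, and 13.1 used alone misclassifies some of them (minor)

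*SAP*

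**What the plan says.** SAP 13.1 covers AEs whose onset has month and year only. The imputed onset is "15th of the month or fist dose date which one comes later. The imputed date will be used to derive TEAE analysis flag". The same section defines the window: "Treatment emergent adverse events (TEAE) are defined as AEs with onset after the start of study medication", ending at last dose + 14 days or the analysis cut-off if that is earlier. The flag decides what is tabulated: "Only treatment-emergent adverse events will be included in summary tables".

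SAP 8.2.1 treats the same AEs differently. It presumes an AE is treatment-emergent, with two exceptions: an onset recorded as falling before or after treatment, and an AE for which "its exclusion from the treatment emergent period can be definitely ascertained from the end date or available month and year components" (those recorded for onset or resolution). A partial onset is compared with first dose as far as possible, with no imputation. No data cut-off is mentioned.

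The start of the window has three wordings. SAP 8.2.1 counts "from the first dose of study drug medication up to and including 14 days after the end of treatment". The same section, on AEs that worsen, speaks of cases where "the onset date is before the start of study treatment [Visit 2 /Day 1 + 1" (a bracketed gloss). SAP 13.1 requires onset after the start of medication. SAP 10.3 sets "Day 1 = the date of the first dose of study drug", and Protocol 9.1.2 allows that date to differ from Visit 2: "The subject may take the first dose of the study medication the same day or the next morning".

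SAP Appendix 2 handles missing dates for medications and AEDs only. SAP section 16 does not mention the AE date rule.

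**The concern.** One flag has two derivations, and they can disagree for the same AE. The flag feeds every AE incidence table in SAP 13.1, including the serious, severe, related and discontinuation tables, in a study whose main purpose is safety.

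If one programmer followed 8.2.1 and the other 13.1, the independent programming in SAP 15.2 would expose the difference. If both followed 13.1, which is the more specific text, they would agree on the same wrong flag. Pre-dose AEs do reach the database, because Protocol 10.1.4 starts AE reporting at Visit 1. Non-serious AEs are collected for 14 days after last dose and SAEs for 30, so both ends of the window matter.

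**Working it through.** The plan gives no figure to reproduce. The check applies each rule to example dates, then counts the calendar dates on which 13.1 can go wrong.

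**Rules**
- 13.1: imputed onset = max(15th of onset month, first dose). The AE is treatment-emergent if this date lies between first dose and min(last dose + 14, cut-off).
- 8.2.1: treatment-emergent unless the month/year or the end date places the AE wholly outside first dose to last dose + 14.

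**Examples (hypothetical dates, no worsening on drug)**

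| Case | Recorded onset | Other dates | 13.1 imputed | 13.1 alone | 8.2.1 |
|---|---|---|---|---|---|
| 1 | April | first dose 5 Apr, AE ended 3 Apr | 15 Apr | flagged | excluded |
| 2 | February | last dose 25 Jan, limit 8 Feb | 15 Feb | dropped | kept |
| 3 | June, on drug | cut-off 10 Jun | 15 Jun | dropped | kept |
| 4a | March | first dose 10 Apr | 10 Apr | flagged if Day 1 counts | excluded |
| 4b | April | first dose 20 Apr, AE ended 12 Apr | 20 Apr | flagged if Day 1 counts | excluded |
| 4c | April, ongoing | first dose 20 Apr | 20 Apr | dropped only if Day 1 does not count | kept |

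Cases 1 to 3 do not depend on how Day 1 is read. In cases 1 and 4b the imputed onset falls after the AE's own end date. Counting Day 1 fails 4a and 4b; not counting it fails 4c. No reading of Day 1 makes 13.1 agree with 8.2.1 throughout.

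**Counts over 365 reference dates (2017 calendar)**

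Onset 1–21 days before first dose, 365 × 21 = 7,665 combinations. The range assumes the full 21 days of screening, which the plan gives as a maximum.
- Earlier month than first dose: 2,772 (36.2%), all imputed exactly to first dose. All are flagged if Day 1 counts.
- Same month: 4,893. Of these, 1,092 (14.2% of 7,665) are imputed after first dose and flagged on either reading. This requires a first dose on day 2–14 (156 of 365 dates).
- The other 3,801 same-month onsets are imputed to first dose and flagged if Day 1 counts.
- A same-month flag is definitely wrong only where an end date precedes first dose. The 1,092 and 3,801 are therefore ceilings.

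Onset 1–14 days after last dose, 365 × 14 = 5,110:
- The 15th lies beyond last dose + 14 in 1,260 (24.7%), affecting 168 of 365 last-dose dates. All of these onsets fall in the month after last dose.

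Onset in the 30 days up to and including a cut-off, 365 × 30 = 10,950:
- The 15th lies beyond the cut-off in 1,260 (11.5%), a mean of 1,260 / 365 = 3.45 days per cut-off date. There are none when the cut-off is on the 15th or later.

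Onset 1–30 days after first dose, 10,950:
- Imputed to first dose in 1,523 (13.9%). These are lost only if Day 1 does not count, and only when first dose is on or after the 15th (197 of 365 dates).

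**The case against.** The strongest defence is a combined reading: apply the definite exclusions of 8.2.1 first, then let 13.1 place what remains. That resolves cases 1, 4a and 4b. It is sensible, but the SAP does not state that order, and 13.1 says its imputed date sets the flag. It also leaves cases 2 and 3, where 8.2.1 would keep the AE and the uncapped date then drops it.

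Four stronger readings are tempting and are not supported.

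- *That 13.1 has no upper limit.* It has one, in its definition of a treatment-emergent AE. Only the imputed date is uncapped.
- *That on-drug AEs early in titration, when hypersensitivity is watched, will be lost.* This needs Day 1 not to count, the less plausible reading: 8.2.1 counts from first dose, and imputing to the first-dose date makes little sense if that date is then excluded. Two-weekly visits with calls between them also make a missing onset day less likely in this period. The on-drug loss and the flagging of earlier-month AEs cannot both occur, since they need opposite readings.
- *That the post-treatment loss in case 2 involves on-drug onsets.* When last dose + 14 falls on day 1–14, the last dose was in an earlier month, so the onsets at issue are in follow-up.
- *That the percentages are error rates for AEs.* They are shares of calendar dates.

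It is also fair that Protocol 10.2 requires an onset date for each AE, that all AEs remain in the by-subject listing with collected dates, and that deaths and non-treatment-emergent SAEs have their own listings. The early cut-off is only a possibility in SAP section 14, and any loss there is confined to that report. These points limit the harm but do not remove the inconsistency.

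**Conclusion.** The point holds and is minor. For month/year-only onsets the SAP gives two rules for one flag and no precedence. Taken alone, 13.1 can flag an AE that ended before first dose. It can also drop an AE that may lie in the window whenever last dose + 14 (168 of 365 last-dose dates) or the cut-off falls on day 1–14 of a month. If Day 1 counts, it also flags every partial-dated AE from a month before first dose, and same-month AEs that ended before first dose.

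The effect on reported incidence cannot be computed, because the documents do not give the number of partial-dated AEs; it is probably small. The calendar counts treat all dates as equally likely and, before first dose, assume a full 21-day screening. The summaries are descriptive and no inference depends on them.

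**What to change.** Make 8.2.1 govern the flag and have 13.1 refer to it, keeping the existing 8.2.1 handling of missing onsets and partial end dates. Then:

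1. State that onset on the first-dose date is treatment-emergent. Delete the bracketed Visit 2/Day 1 + 1 term, or define it as the first-dose date.
2. For month/year-only onsets, first exclude an AE whose month/year or end date (full or partial) definitely places it before first dose, unless it worsened on drug. Also exclude one whose onset month begins after the earlier of last dose + 14 and any data cut-off. Flag the rest.
3. If an imputed date is still wanted for other derivations, use the later of the 15th and first dose, capped at the earliest of the AE end date, last dose + 14 and the data cut-off.

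This uses only recorded onset, end and dosing dates and the cut-off. No report date is needed, and none is among the AE fields listed in 8.2.1.

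The cost is wording in two sections and a small change to the flag derivation, with no new data. SAP section 4 allows revision before database lock. The downside to state is that some partial-dated onsets beyond the window would be counted:
- Days 15–30 after last dose: 4,208 instead of 1,523 of 5,840 (365 × 16) combinations, an extra 2,685. These are mainly SAEs, since other AEs are collected only to day 14.
- Days 1–30 after an early cut-off: up to 5,373 instead of 1,523 of 10,950, an extra 3,850 at most.

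Both err in the conservative direction, in keeping with the way 13.1 already treats missing severity and relationship.

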10 SAFETY AND ADVERSE EVENTS

10.1 Definitions

10.1.1 *Adverse Events*

An adverse event (AE) is any symptom, sign, illness, or experience that develops or worsens in severity during the course of the study. Intercurrent illnesses or injuries should be regarded as AEs. Abnormal results of diagnostic procedures are considered to be AEs if the abnormality:

- Results in study withdrawal
- Is associated with an SAE
- Is associated with clinical signs or symptoms
- Leads to additional treatment or to further diagnostic tests
- Is considered by the investigator to be of clinical significance

10.1.2 *Serious Adverse Event*

AEs are classified as serious or non-serious. A *serious adverse event* is any AE that is:

- Fatal
- Life-threatening
- Requires or prolongs hospital stay
- Results in persistent or significant disability or incapacity
- A congenital anomaly or birth defect
- An important medical event

Important medical events are those that may not be immediately life threatening but are clearly of major clinical significance. They may jeopardize the subject and may require intervention to prevent one of the other serious outcomes noted above. For example, drug overdose or abuse, a seizure that did not result in inpatient hospitalization, or intensive treatment of bronchospasm in an emergency department would typically be considered serious.

10.1.3 *Suspected Adverse Reaction*

Suspected adverse reaction means any AEs for which there is a reasonable possibility that the drug cause the AE. For the purpose of investigational new drug (IND) safety reporting, “reasonable possibility” means there is evidence to suggest a causal relationship between the drug and AE. Suspected adverse reaction implies a lesser degree of certainty about causality than adverse reaction, which means any AE caused by a drug.

All AEs that do not meet any of the criteria for seriousness should be regarded as *non-serious AEs*.

10.1.4 *Adverse Event Reporting Period*

The study period during which AEs must be reported is normally defined as the period from the initiation of any study procedures (Visit 1) to the end of the study treatment follow-up. For this study, the AE reporting period is defined as 30 days following the last administration of study treatment for SAEs. For all other AEs, reporting period is defined as 14 days following the last administration of study treatment.

10.1.5 *Preexisting Condition*

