12.4 Safety Variable Analyses

All enrolled subjects who took at least one dose of study drug medication will be evaluable for safety. The number and percent of subjects reporting AEs (including treatment-emergent laboratory abnormalities) will be tabulated for all safety evaluable subjects and by the 3 subgroups of subjects defined in Section 12.2. All serious AEs (SAEs) will be tabulated separately as well as included with all reported AEs.

Physical and neurologic assessments, laboratory results, vital signs (including orthostatic measurements, weight and height), concomitant medications, ECGs, and C-SSRS will be summarized using descriptive statistics.

Extent of exposure and dose modifications will be tabulated.

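### New-onset SAEs on days 15–30 after the last dose are collected and listed but counted in no incidence table, and the SAP does not record this departure from the protocol

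*SAP*

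**What the plan says.** Protocol 10.1.4 sets two post-dose windows. For serious events, "the AE reporting period is defined as 30 days following the last administration of study treatment for SAEs". For the rest, "For all other AEs, reporting period is defined as 14 days following the last administration of study treatment". Protocol 12.4 then states the analysis: "All serious AEs (SAEs) will be tabulated separately as well as included with all reported AEs". That sentence carries no treatment-emergent restriction and no day limit.

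The SAP uses one window for everything. Section 8.2.1 counts events as treatment-emergent "up to and including 14 days after the end of treatment", and section 13.1 gives the same 14-day limit. Section 13.1 also states the rule for outputs: "Only treatment-emergent adverse events will be included in summary tables". The only SAE table planned there is "Incidence of treatment-emergent serious adverse events by MedDRA System Organ Class and Preferred Term". Deaths have a listing but no table.

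Later serious events are covered by listings. Section 13.1 puts every reported event in a by-subject listing whether or not it is treatment-emergent, and also plans a "Listing of subjects with non treatment-emergent serious adverse events" and a listing of subjects who died.

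SAP section 4 says that the SAP replaces the protocol's statistical text and that it identifies substantial differences. Section 16 is where changes are recorded. It mentions one departure from Protocol 12.4 (orthostatic vital signs) and says nothing about the SAE window.

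**The concern.** The protocol chose a longer window for serious events than for other events, and the SAP applies the shorter one to both. Data gathered on purpose for days 15–30 then never reach a numerator.

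This matters because long-term safety is one of the study's stated objectives and the analysis is descriptive only. The incidence tables are the main quantitative safety result, and they are what summaries and pooled analyses will draw on. A listing gives no count and no percentage. SAE reporting starts at Visit 1, so the non-treatment-emergent listing also combines events before the first dose with events after day 14.

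Counts of specific serious events are likely to be low, so a few cases can change a rate. One event is 0.1 percentage points among 1,000 subjects (1/1,000). It is 5 points in a phenytoin or phenobarbital subgroup at its planned minimum of 20 (1/20).

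**Working it through.** The plan gives no figure for this point, so there is none to reproduce. The check is window arithmetic plus tracing which output each event reaches.

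**Inputs**
- SAE collection after the last dose: 30 days (Protocol 10.1.4).
- Collection of other adverse events after the last dose: 14 days (Protocol 10.1.4).
- Treatment-emergent window after the last dose, all events: 14 days (SAP 8.2.1 and 13.1).
- Last scheduled visit: 14 days after the last dose (Protocol 9.1.15).

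**Days outside the table**
- Collected but not tabulated: 30 − 14 = 16 days (days 15 to 30).
- Share of the post-dose SAE window: 16/30 = 53.3%. The SAE table covers the other 14/30 = 46.7%.
- For non-serious events: 14 − 14 = 0 days. The mismatch affects serious events only.

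**The same 16 days against follow-up from first dose**
- Stopping after 365 days of dosing: 16/(365 + 30) = 16/395 = 4.1%.
- Stopping after the 12-week titration (84 days): 16/(84 + 30) = 16/114 = 14.0%.
- Still on treatment at the data cut-off: 0%.

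**Where an SAE goes, by onset date**

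| Onset | SAE incidence table | Listings |
|---|---|---|
| On treatment, including taper | Yes | All-AE; treatment-emergent SAE; deaths if fatal |
| Days 1–14 after last dose | Yes | As above |
| Onset by day 14, becomes serious later | Yes, if kept as one event with its onset date | As above |
| New onset, days 15–30 | **No** | All-AE; non-treatment-emergent SAE; deaths if fatal |

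The taper entry assumes that the last dose date includes taper doses. Protocol 6.1.2.3 supports this by placing the follow-up visit 14 days after the last dose, following taper.

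**Number of events**

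The documents give neither the number of subjects who will stop treatment nor a post-dose SAE rate. For scale only, assume a constant post-dose hazard, D subjects off drug and a 30-day SAE risk r. Untabulated SAEs are then about D × r × 16/30.
- D = 300, r = 0.5%: 300 × 0.005 × 16/30 = 0.8.
- D = 300, r = 5%: 300 × 0.05 × 16/30 = 8.0.
- Across D = 100 to 500 and r = 0.5% to 5%: about 0.3 to 13.

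These values of D and r are assumptions, not plan figures, and full ascertainment to day 30 is also assumed.

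**The case against.** The case for leaving the tables as they are has real substance.

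- **There is a reason for 14 days.** The last scheduled visit is 14 days after the last dose. Beyond that, ascertainment rests on subjects reporting events that they believe may be related, so one table spanning both periods would mix active and passive follow-up. This stands. It is a reason to show days 15–30 separately, not to leave them uncounted.
- **The safety endpoint is worded in treatment-emergent terms.** Protocol 6.2.2 and 9.3 use that wording. Neither sets a 14-day limit for serious events, though, and 12.4 speaks of all SAEs.
- **Taken literally, all SAEs would include those before the first dose.** True, since reporting starts at Visit 1. A table running from first dose to last dose + 30 days meets the commitment for post-dose events only. Section 16 should say that pre-dose SAEs stay in listings.
- **The SAP supersedes the protocol's statistical text.** It does, but it also says that it identifies substantial differences. One can argue over whether this one is substantial. It narrows an explicit commitment, and section 16 does record the orthostatic change to the same protocol section.

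Three stronger readings are tempting, and the documents do not support them.

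- A reader might infer that about half of all SAEs are dropped. The 53% is a share of post-dose calendar days, not of events.
- A reader might infer that later SAEs and deaths disappear, or sit only in one mixed listing. They also appear in the all-AE listing and, if fatal, in the deaths listing. Start dates and study days allow pre-dose and post-dose events to be told apart.
- A reader might infer that a reaction developing when the drug is stopped is missed. The flag follows the onset date, so an event that began on drug, during taper or by day 14 stays in the table even if it becomes serious later.

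**Conclusion.** The point holds in limited form. SAEs with new onset on days 15–30 after the last dose are collected and listed, but they enter no incidence table. This falls short of Protocol 12.4, and SAP section 16 does not disclose it. The gap is 16 of 30 post-dose collection days for each subject who stops treatment and is followed to day 30 before the data cut-off.

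The number of events cannot be derived from the documents and is probably small. That judgement rests on the onset-date rule, on taper doses counting towards the last dose date, and on most SAEs arising on treatment. Nothing here suggests that SAEs are hidden or that the SAE rate is grossly understated. The change is worth making because the data already exist and the protocol promised the count.

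**What to change.** 1. Keep the 14-day treatment-emergent tables as planned.
2. In SAP 13.1, add a tabulation of SAEs and deaths from first dose to last dose + 30 days (or the analysis cut-off if sooner), overall and by the three subgroups. Alternatively, add a separate count of SAEs and deaths with onset on days 15–30. In either form, footnote that no visit is scheduled after day 14, so the later period is passively ascertained.
3. State in SAP 13.1 that the last dose date includes taper doses.
4. Record both windows in SAP section 16 with the reason, and note that pre-dose SAEs are listed only.

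The cost is one derived flag, one more table and a few sentences. No new data are needed and study conduct does not change. The SAE count may rise slightly, and readers will see two SAE figures, so each must carry its window in the title.
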